6.2.2 Treatment period

Safety evaluation visits are to be conducted after the initiation of afatinib (Giotrif®), at Day 28 (-7/+2)/Visit 2 and every 28 (-7/+2) days onwards. Additional safety evaluation visits may be conducted as necessary, at the investigator's discretion. The investigator is responsible for determining the necessity and frequency of the additional safety visits as well as the extent of the evaluation (physical examination, laboratory testing, etc.) at each visit.

Table 6.2.2: 1 Visit 2/Day 28 (-7/+2) and every 28 (-7/+2) days onwards - treatment and safety evaluation

	The following must be performed and information recorded in the patient's chart	What to include in eCRF
Physical examination	Physical examination results (see Flow Chart). The evaluation of the ECOG performance score will be performed.	Verify that this physical examination was performed and record results (see Flow Chart).
Disease Assessment	Disease Assessment will be based on the assessment of cancer related symptoms and, if available, radiologic assessments as per standard of care at the site.	Disease Assessment to be included on CRF.
ECG	ECGs may be performed at the discretion of the investigator.	Verify if an ECG was performed prior to or during any safety evaluation.
LVEF (Left Ventricular Ejection Fraction)	Cardiac left ventricular function assessment by either ECHO or MUGA only for patients with cardiac risk factors and those with condition that can affect LVEF, at the discretion of the investigator and in accordance to the current standard of care.	Verify if an ECHO (or MUGA) was performed prior to or during this visit. Verify that LVEF has not deteriorated to CTCAE Grade ≥3. If CTCAE Grade ≥3, see Section 4.1.4.1
Safety Laboratory Testing – Optional	Hematology, and Biochemistry examination. See Section 5.2.3 for recommended safety laboratory evaluations. Laboratory testing is optional at this visit and may be performed at the discretion of the investigator and in accordance to the current standard of care. Refer to Section 5.2.3 for a list of recommended safety laboratory tests. If performed as part of a safety evaluation visit, the test results must be filed or recorded in the patient's chart.	Verify if all recommended safety laboratory testing was performed and that values were acceptable according to the protocol. If not, see Sections: 4.1.4.1 and 5.2.2.1 No lab values are to be recorded on the CRF.
Urine Examination – Optional	Urine examination. See Section 5.2.3 for recommended urine examinations. Urine Examination is optional at this visit and may be performed at the discretion of the investigator and in accordance to the current standard of care.	Verify if all recommended urine testing was performed. No values from the urine examination are to be recorded on the CRF.

Table 6.2.2: 1 (continued) Visit 2/Day 28 and every 28 (-7/+2) days onwards - treatment and safety evaluation (Page 2 of 2)

	The following must be performed and information recorded in the patient's chart	What to include in eCRF
Adverse events	Patients should be asked to report any hospitalizations, emergency treatments, or new medications as well as any general health issues that may have surfaced since their last visit. All the information collected should be recorded in the patient's chart. Refer to Sections: 5.2.2 and 5.2.2.2 for protocol specific requirements regarding the collection and reporting of adverse event information.	All relevant AEs and all SAEs.
Compliance	Check number of tablets remaining and that trial medication was taken correctly, collect any used bottles of afatinib (Giotrif®).	Record if the patient is taking the medication according to the protocol.
Concomitant Medications	Patients should be asked to report any concomitant drug use (including, but not limited to,: non-prescription medications, anaesthetic agents, homeopathic/herbal remedies and dietary supplement preparations)	No concomitant medications will be recorded on eCRFs.
Dispense Trial Medication	Dispense sufficient medication for the next cycle of treatment (see Section 4.1.4).	Record: dose dispensed, medication numbers of bottles dispensed, and only the start date of any dose changes (if applicable).
Contact	A contact is required 15 (±3) days after the patient's first dose to assess AEs and dose reductions.	Record when this contact took place.

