- 2 Includes vital signs (pulse, blood pressure), temperature, height (cm), weight (kg) and an ECOG performance score
- 3 ECG/LVEF to be conducted for patients with cardiac risk factors at the discretion of the investigator and in accordance to the current standard of care. In patients with ejection fraction below the institution's lower limits of normal, cardiac consultation as well as afatinib (Giotrif®) treatment interruption or discontinuation should be considered.
- 4 Safety laboratory testing: haematology, biochemistry and urine examinations (see Section 5.2.3). All laboratory tests mentioned in Table 5.2.3: 1 are required to be performed at screening and are recommended to be performed at the discretion of the investigator and in accordance to the current standard of care.
- Urine examinations (see Table 5.2.3: 1) are required to be performed at screening and are recommended to be performed at the discretion of the investigator and in accordance to the current standard of care.
- 6 Beta-Human Chorionic Gonadotropin (β-HCG) testing in urine or serum in women of childbearing potential. A negative result is required for inclusion in the trial.
- D Provide a diarrhoea diary with drug supply at cycle 1 and 2. Data on diaries should be checked by the study staff against AEs and Appendix 10.1.1.
- P A contact is required 15 (±3) days after the patient's first dose to assess AEs and dose reductions.
- O Indicates a recommended/optional test or procedure according to patient's course as required by clinical condition
- ** EOT(V): end of treatment (visit) with trial medication.
- # FU (V): Follow-up visit (end of observational phase) which should occur 28 days after the end of treatment (EOT) visit This visit can be conducted by a phone call.
- Within 28 days after last trial drug administration all AEs will be collected and documented. SAEs must always be collected, documented, and reported within this 28 day time period. The investigator does not need to actively monitor patients for adverse events once the clinical trial has ended. However, if the investigator becomes aware of an SAE(s) that occurred after the patient has completed the clinical trial (including any protocol required REP and / or follow-up), it should be reported by the investigator to the sponsor if considered relevant by the investigator.

Proprietary confidential information.

Boehringer Ingelheim 08 Feb 2021 BI Trial No.: 1200.55

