4.1.4.1 Dose reduction scheme

Treatment related adverse events will be managed by treatment pauses and subsequent dose reductions of afatinib (Giotrif®) according to the schedule described in Table 4.1.4.1: 1.

Dose reductions will apply to individual patients only. Once the dose has been reduced, it cannot be increased later.

The investigator is responsible for determining the necessity and frequency of any additional/unscheduled visits as well as the extent of the evaluation (e.g., physical examination, laboratory testing, adverse events, etc.) performed at these visits. At a minimum the investigator should note in the patient's chart when an additional/unscheduled visit occurs and make relevant entries on the AE and medication dispensing eCRFs.

To prevent the development of more severe adverse events, treatment related diarrhoea, nausea and vomiting or rash should be managed early and proactively as described in Appendix 10.1.

Table 4.1.4.1: 1 Dose reduction scheme

Action	Dose Reduction Scheme
Pause treatment until	Resume with dose reduction by 10mg
1	decrements.
_	If patient cannot tolerate 20mg/day,
baseline.	permanent discontinuation of afatinib (Giotrif®) should be considered.
Resume treatment at a	(Glottis) should be considered.
reduced dose	
according to the Dose	
Reduction Column.	
TC	
weeks trial treatment	
must be permanently	
discontinued ² .	
	If ILD is ruled out as a cause of
	symptoms, grade symptoms and
	relatedness and report as AEs. If AEs are not related, resume afatinib
completed.	(Giotrif®) at current dose. If AEs are
	drug related, follow directions in row
	above.
	If ILD is confirmed, discontinue afatinib
Damaaantly	(Giotrif®).
	INA
	Pause treatment until patient has recovered to Grade ≤1 or baseline¹. Resume treatment at a reduced dose according to the Dose Reduction Column. If patient has not recovered to Grade ≤1 or baseline¹ within 6 weeks trial treatment must be permanently

^{*} The intensity of clinical adverse events graded by the Common Terminology Criteria for Adverse Events v 3.0 (CTC-AE)

After treatment pause due to adverse events, treatment at a reduced dose (i.e., with a new bottle of medication) will restart at the predefined schedule/cycle (i.e., 28 days (-7/+2 days) on the new dose).

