5.2.5.3 Left ventricular function

Left Ventricular Ejection Fraction (LVEF) as measured by Echocardiography (ECHO) or Multiple Gated Acquisition scan (MUGA) will be assessed if clinically indicated. The testing of this function and cardiac monitoring should be considered in patients that develop relevant cardiac signs/symptoms during treatment. In patients with an ejection fraction below the institution's lower limit of normal, cardiac consultation as well as afatinib treatment interruption or discontinuation should be considered.

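### The on-treatment visit table checks LVEF at CTCAE Grade ≥3, the flow chart and Section 5.2.5.3 use the institutional lower limit of normal, and nothing says how the two triggers relate

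*Protocol*

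**What the plan says.** Three places in the current protocol bear on what a site does with an on-treatment LVEF result.

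- **Table 6.2.2: 1 (Section 6.2.2), LVEF row, eCRF column.** After asking whether an echocardiogram or MUGA scan was done, it says "Verify that LVEF has not deteriorated to CTCAE Grade ≥3. If CTCAE Grade ≥3, see Section 4.1.4.1". It gives no other LVEF threshold and does not cite Section 5.2.5.3.
- **Flow Chart footnote 3 and Section 5.2.5.3.** The footnote's condition and measures are "ejection fraction below the institution's lower limits of normal, cardiac consultation as well as afatinib (Giotrif®) treatment interruption or discontinuation should be considered". Section 5.2.5.3 says nearly the same of those "with an ejection fraction below the institution's lower limit of normal, cardiac consultation as well as afatinib treatment interruption or discontinuation should be considered". Neither mentions a CTCAE grade.
- **Section 4.1.4.1, the target of the cross-reference.** Its running text opens with a general rule that rests on the section's own table: "Treatment related adverse events will be managed by treatment pauses and subsequent dose reductions of afatinib (Giotrif®) according to the schedule described in". One readable action cell of that table says "Resume treatment at a reduced dose according to the Dose Reduction Column". The readable text names neither LVEF nor cardiac function.

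The LVEF rows of Table 6.2.1: 1 (screening) and Table 6.2.3: 1 (end of treatment) ask only whether the scan was done. They carry no grade check.

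**The concern.** Site staff complete the eCRF from the visit table. On LVEF, that table asks a different question from the footnote and the section that describe what to do about a low ejection fraction. A result can clear the check in the table while it meets the condition in the footnote. At Grade ≥3 the table sends the site to a section whose explicit LVEF rule has been taken out, while Section 5.2.5.3 lists measures of its own.

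What is at stake is uniform handling of a cardiac safety finding across up to 200 sites. The statistical results are not at stake.

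**Working it through.** No arithmetic applies. The check sets the current passages side by side and then traces where the cross-reference came from.

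**Step 1: cross the two triggers.** Each is a yes/no condition, which gives four cases.

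| Below institutional limit? | CTCAE Grade ≥3? | Footnote 3 and Section 5.2.5.3 | Table 6.2.2: 1 |
|---|---|---|---|
| No | No | Not triggered | Check passed |
| Yes | No | Consultation, pausing or stopping to be considered | Check passed, no prompt |
| Yes | Yes | Same measures to be considered | Go to Section 4.1.4.1 |
| No | Yes | Not triggered | Go to Section 4.1.4.1 |

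The passages agree in the first case only. In the second, the footnote and 5.2.5.3 apply and the table is silent. In the third, both apply and each names its own route. Whether the fourth can occur, and how wide the second is, cannot be settled here: the protocol and SAP give no CTCAE grade boundaries for LVEF, and each institution sets its own lower limit.

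**Step 2: look for a sentence that connects the triggers.** None was found in the Flow Chart, Section 4.1.4.1, Section 5.2.5.3 or Section 6.2.2. The removal criteria in Section 3.3.4.1 contain no LVEF item.

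**Step 3: trace the cross-reference.** The amendment log in Section 11 describes superseded text and is used here only as history. Under Amendment 1 it records that:

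- the LVEF Grade ≥3 discontinuation sentence was deleted from Section 4.1.4.1;
- the matching criterion was deleted from Section 3.3.4;
- an LVEF verification was deleted from the screening table;
- the LVEF wording of all three visit tables was limited to patients with cardiac risk factors or a condition that can affect LVEF.

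It records no change to the Grade ≥3 check in Table 6.2.2: 1, and the check stands in the current text.

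**Step 4: ask whether the cross-reference still works.** This stays open. The column of Table 4.1.4.1: 1 that names the event and grade for each row was lost when the PDF was read. A general row for drug-related events of Grade ≥3, or even a row for LVEF, may be there.

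**Step 5: look for an effect on the analysis.** SAP Section 7.8.3 lists LVEF results and flags a fall of at least 20% from baseline that also lies under the site's lower limit, with 50% used where that limit is missing. This is a third threshold, but it only marks a listing and governs no treatment. The primary endpoint in SAP Section 5.1 is the number of patients with adverse events and does not depend on any of these triggers.

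**The case against.** The best reply is that two thresholds need not conflict. The footnote and Section 5.2.5.3 are advisory: they ask that measures be considered. The visit table is an eCRF verification at a toxicity grade. An early advisory level and a later graded check can work together, and pausing treatment under 4.1.4.1 is compatible with interruption under 5.2.5.3. The reference may also be generic, because the next row of the same table sends unacceptable laboratory values to 4.1.4.1 as well. Amendment 1 edited this very row and left the check in, and the log does not say whether that was intended. Finally, Sections 6.1.2 and 6.2 direct sites to the Flow Chart, so footnote 3 still applies at every visit.

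Most of this stands, and it rules out several stronger readings that a reader might infer:

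- **That the cross-reference is dead, or leads at most to the general pause-and-reduce scheme.** The lost column prevents either conclusion, and a loss in PDF reading is not a gap in the plan.
- **That the two routes prescribe different management.** The footnote and 5.2.5.3 prescribe nothing; they ask for consideration.
- **That every patient between the institutional limit and Grade 3 is treated differently by the two passages.** The table is silent on such patients, and the footnote and 5.2.5.3 continue to cover them.

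The objection does not supply the missing link. A tiered arrangement is possible, but the protocol does not describe one, and a site using the visit table alone would not learn of the lower-limit trigger.

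**Conclusion.** The point holds as a minor inconsistency. The on-treatment table keeps a Grade ≥3 LVEF check that points to Section 4.1.4.1, although the explicit LVEF rule there and its counterpart in 3.3.4 were removed and the other two visit tables have no such check. The footnote and Section 5.2.5.3 use the institutional lower limit, and nothing states how the two triggers relate.

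The practical gap is a missing prompt: a patient under the institutional limit but not at Grade ≥3 is covered by the footnote and 5.2.5.3 and not flagged by the visit table. The number of such patients cannot be derived, because LVEF is measured at the investigator's discretion in selected patients and the grade boundaries are not in the documents. Sample size, endpoints and planned analyses are unaffected.

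The trigger mismatch rests on current text and does not depend on the lost column. The status of the cross-reference does depend on it and has to be checked against the full Table 4.1.4.1: 1.

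**What to change.** Reconcile the LVEF row of Table 6.2.2: 1 with Flow Chart footnote 3, Section 5.2.5.3 and Section 4.1.4.1. Either use one trigger throughout, or keep both and state in the table how they relate and where each leads. Check the reference to 4.1.4.1 against the complete table there, then confirm or correct it. Which trigger and which action apply is for the sponsor to decide.

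The cost is the wording of one table cell, at the next amendment or in a letter to sites. No data collection or analysis need change.

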5.2.2 Assessment of adverse events

5.2.2.1 Definitions of adverse events

Safety assessments will consist of monitoring and recording all adverse events (AEs) and serious adverse events (SAEs) and includes daily record of diarrhea status as reported by the patient for the first two cycles. In addition, the investigator does not need to actively monitor patients for adverse events once the clinical trial has ended. However, if the investigator becomes aware of an SAE(s) that occurred after the patient has completed the clinical trial (including any protocol required REP and / or follow-up), it should be reported by the investigator to the sponsor if considered relevant by the investigator.

Adverse event

An adverse event (AE) is defined as any untoward medical occurrence, including an exacerbation of a pre-existing condition, in a patient in a clinical investigation who received a pharmaceutical product. The event does not necessarily have to have a causal relationship with this treatment.

Serious adverse event

A serious adverse event (SAE) is defined as any AE which results in death, is immediately life-threatening, results in persistent or significant disability / incapacity, requires or prolongs patient hospitalisation, is a congenital anomaly / birth defect, or is to be deemed serious for any other reason if it is an important medical event when based upon appropriate medical judgement which may jeopardise the patient and may require medical or surgical intervention to prevent one of the other outcomes listed in the above definitions.

The following hospitalizations are not considered to be serious adverse events (SAEs) because there is no "adverse event" (i.e., there is no untoward medical occurrence) associated with the hospitalization:

- Hospitalizations for respite care
- Hospitalization planned prior to informed consent (where the condition requiring the hospitalization has not changed post trial drug administration)

Intensity of adverse event

The intensity of adverse events should be classified and recorded according to the Common Terminology Criteria for Adverse Events (CTCAE) version 3.0 in the eCRF.

Causal relationship of adverse event

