Medical judgment should be used to determine the relationship, considering all relevant factors, including pattern of reaction, temporal relationship, de-challenge or re-challenge, confounding factors such as concomitant medication, concomitant diseases and relevant history. Assessment of causal relationship should be recorded in the case report forms.

Doc. No.: U13-1326-02 Trial Protocol Page 42 of 95

Yes: There is a reasonable causal relationship between the investigational product

administered and the AE.

No: There is no reasonable causal relationship between the investigational product

administered and the AE.

Worsening of the underlying disease or other pre-existing conditions

Worsening of the underlying disease or of other pre-existing conditions will be recorded as an (S)AE in the eCRF.

If progressive disease occurs and is associated with symptoms, the term "Progressive Disease" should not be reported as AE, however, signs and symptoms of progressive disease will be reported as an (S)AE (if applicable). Exception to this: Death due to progressive disease and where no signs or symptoms are available should be reported as "malignant neoplasm progression (grade 5, outcome fatal)."

Changes in vital signs, ECG, physical examination, and laboratory test results

Changes in vital signs, ECG, physical examination and laboratory test results will be recorded as an (S)AE in the (e)CRF, if they are judged clinically relevant by the investigator.

Expected Adverse Events

For expected (listed) AEs of afatinib (Giotrif®), see the current version of the IB (U03-3218).

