5.2.2.2 Adverse event and serious adverse event reporting

The residual effect period (REP) for this trial is defined as 28 days after last intake of study drug.

Table 5.2.2.2:1 AE/SAE reporting requirements

Time period	Reporting requirements
From signing of informed consent to ≤28 days after last trial drug administration	Report all AEs and SAEs regardless of relatedness or whether the trial drug was administered. This includes all deaths.

hringer Ingelheim 08 Feb 2021

Doc. No.: U13-1326-02 Trial Protocol Page 43 of 95

Table 5.2.2.2:1 (continued) AE/SAE reporting requirements

Post-treatment (>28 days after last trial drug	The investigator does not need to actively
administration)	monitor patients for adverse events once the
	clinical trial has ended. However, if the
	investigator becomes aware of an SAE(s) that
	occurred after the patient has completed the
	clinical trial (including any protocol required
	REP and / or follow-up), it should be
	reported by the investigator to the sponsor if
	considered relevant by the investigator.

BI has set up a list of AEs which are defined to be always serious. In order to support the investigator with the identification of these "always serious adverse events", if a non serious AE is identified to be serious per BI definition, a query will be raised. The investigator must verify the description and seriousness of the event. If the event description is correct, the item "serious" needs to be ticked and an SAE has to be reported in expedited fashion following the same procedure as above. The list of these adverse events can be found via the RDC-system.

The investigator must report the following events using the SAE form immediately (within 24 hours) to the sponsor: SAEs, non-serious AEs relevant to a reported SAE, adverse events of special interest. Further details regarding AE reporting procedure are provided in the ISF.

Pregnancy

Pregnancy is an exclusion criterion in this trial.

In rare cases, pregnancy might occur in clinical trials and observational trials. In such cases the actions delineated in Table 4.2.3: 1 should be followed.

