8.3.1 Source documents

Source documents provide evidence for the existence of the patient and substantiate the integrity of the data collected. Source documents are filed at the investigator's site.

Data reported on Electronic Case Report Forms (eCRFs) that are transcribed from source documents must be consistent with the source documents or the discrepancies must be explained. The investigator may need to request previous medical records or transfer records, depending on the trial; also current medical records must be available.

For eCRFs all data must be derived from source documents.

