8.3.2 Direct access to source data and documents

The investigator/institution will permit trial-related monitoring, audits, IRB/IEC review and regulatory inspection, providing direct access to all related source data/documents. CRFs/eCRFs and all source documents, including progress notes and copies of laboratory and medical test results must be available at all times for review by the sponsor's clinical trial monitor, auditor and inspection by health authorities (e.g., Food and Drug Administration (FDA). The Clinical Research Associate (CRA)/on site monitor and auditor may review all CRFs/eCRFs, and written informed consents. The accuracy of the data will be verified by reviewing the documents described in Section 8.3.1.

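### Four visit tables ask for only *relevant* non-serious AEs in the eCRF, while Section 5.2.2 requires all AEs up to 28 days after the last dose

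*Protocol*

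**What the plan says.** **Visit tables.** Protocol Tables 6.2.1:1 (screening), 6.2.2:1 (treatment visits), 6.2.3:1 (end of treatment) and 6.2.4:1 (follow-up) each have one column for the patient's chart and one for the eCRF. In the adverse-event row, the eCRF column reads the same in all four: "All relevant AEs and all SAEs". The chart column is broad and, at treatment visits, ends with a pointer: "Refer to Sections: 5.2.2 and 5.2.2.2 for protocol specific requirements regarding the collection and reporting of adverse event information". At screening the pointer names Section 5.2.2 twice and omits 5.2.2.2.

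**AE sections.** Section 5.2.2.1 begins: "Safety assessments will consist of monitoring and recording all adverse events (AEs) and serious adverse events (SAEs"). Table 5.2.2.2:1 says, for the time from consent to 28 days after the last dose: "Report all AEs and SAEs regardless of relatedness or whether the trial drug was administered". Beyond 28 days it asks only for SAEs that the investigator learns of and considers relevant.

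**Flow chart.** Note 7 says "Within 28 days after last trial drug administration all AEs will be collected and documented". It is attached to the follow-up column only.

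**Use in the analysis.** SAP 5.1 makes the number of patients with AEs the primary endpoint. SAP 7.8.1 plans frequencies by preferred term for all grades, and a table of AEs with an incidence above 5%.

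**The concern.** AEs are the main data of this trial, and the protocol gives two rules for which of them go into the database. The AE sections say all. The eCRF cell says *relevant* for AEs and, next to it, *all* for SAEs. That contrast makes it hard to treat the word as filler. A site working from the visit table could enter everything in the chart and then pass on only the non-serious events that it thinks matter.

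An event filtered in this way would leave little other trace. Laboratory values are not collected (SAP 7.8.2), and for ECGs only the date of the tracing is (SAP 7.8.4). Diarrhoea and rash are better covered. The diarrhoea diary is checked against reported AEs for the first two cycles (Protocol 5.3.2.1), and SAP 7.2 says that therapies for rash and diarrhoea are on the eCRF, although the visit tables say that no concomitant medication is entered there. What is at stake is the reported frequency of other non-serious events, mostly of low grade.

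**Working it through.** **1. The instructions side by side**

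| Place in the protocol | Period or visit | Which AEs |
|---|---|---|
| Section 5.2.2.1 | general | all AEs and SAEs |
| Table 5.2.2.2:1, first row | consent to 28 days after last dose | all AEs and SAEs |
| Table 5.2.2.2:1, second row | later than 28 days | SAEs the investigator learns of and considers relevant |
| Flow chart, note 7 | 28 days after last dose (follow-up column) | all AEs |
| Tables 6.2.1:1, 6.2.2:1, 6.2.3:1, 6.2.4:1, eCRF column | each visit | relevant AEs, all SAEs |

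For the screening, treatment and end-of-treatment visits, the conflict rests on Section 5.2.2.1 and Table 5.2.2.2:1. Those two are enough. Note 7 adds support only for the period after the last dose.

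**2. Is *relevant* explained elsewhere?** The cells do not define it. Section 5.2.2.1 uses the idea to limit the recording of non-serious events in one place: changes in vital signs, ECG, physical examination and laboratory results are recorded "if they are judged clinically relevant by the investigator". That is a filter on test changes and not a definition for AEs in general. The other uses in Section 5.2.2 concern late SAEs, and non-serious AEs connected with a reported SAE. None of them limits routine AE entry.

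**3. When does follow-up fall?** End of treatment is 0 to 14 days after the last dose (Section 6.1.3). Follow-up is 28 days, less up to 7, after that visit (Section 6.1.4), so 21 to 28 days.

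- Earliest: 0 + 21 = 21 days after last dose
- Latest: 14 + 28 = 42 days after last dose

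Follow-up can therefore come before or after the 28-day limit. An unqualified *all AEs* in Table 6.2.4:1 would ask for more than Table 5.2.2.2:1 does.

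**4. Where is the 5% cut?** The synopsis gives 481 entered patients, and Section 3 of the protocol defines entered patients as treated.

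- 0.05 × 481 = 24.05, so more than 5% means at least 25 patients.
- 25/481 = 5.20%; 24/481 = 4.99%.

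A term drops out of the table when omissions bring it down to 24 patients:

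| Patients who truly had the term | Share of 481 | Omissions needed |
|---|---|---|
| 25 | 5.2% | 25 − 24 = 1 |
| 30 | 6.2% | 30 − 24 = 6 |
| 36 | 7.5% | 36 − 24 = 12 |
| 48 | 10.0% | 48 − 24 = 24 |

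These figures are distances from the cut. They would be the same for any cause of data loss, and they do not measure an effect of this wording. The documents give no omission rate, and none is assumed.

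**5. The any-AE count.** One entered AE is enough to count a patient. In the earlier phase II trial, 96.7% of the 30 patients who started on 40 mg reported diarrhoea alone (Protocol 2.3). Losing some other non-serious events would rarely change whether a patient is counted.

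**The case against.** The strongest reply is that there is no competing rule, only loose wording. The chart column gathers general health information, much of which is not an AE, and then sends the site to Section 5.2.2. *Relevant* could simply mean whatever that section makes reportable, since it leaves out test changes without clinical relevance and the term Progressive Disease. Data on the eCRF "must be consistent with the source documents or the discrepancies must be explained" (Section 8.3.1), and Section 8.3.2 adds: "The accuracy of the data will be verified by reviewing the documents described in Section 8.3.1".

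Part of this stands. The pointer puts the governing rule within reach, and many sites may have entered everything. But the pointer is in the chart column and not in the eCRF cell, and the reading does not explain why that cell says *all* for SAEs and not for AEs. The verification text covers the accuracy of the data; it does not describe a search of charts for events that were never entered. An AE left out as not relevant could look compliant with the visit table.

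A reader might go further and infer that sites did filter AEs, or that the primary endpoint is understated. The documents support neither. They contain no evidence of filtering, and step 5 suggests that the any-AE count would move little.

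**Conclusion.** The inconsistency is real, is in current text and appears in all four tables. It is minor. It rests on a plain reading of the eCRF cell against Section 5.2.2.1 and Table 5.2.2.2:1, and that part is firm. The consequence is less certain. If a site followed the cell literally, non-serious AEs would be under-recorded, and this would show in the all-grades frequencies by preferred term and in the above-5% table. The size cannot be estimated from the documents. The arithmetic assumes 481 treated patients and says only that terms just above 25 patients are sensitive to a few omissions.

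**What to change.** 1. In the eCRF column of the four tables, and in any eCRF instructions that repeat it, write: *All AEs and all SAEs, for the reporting periods in Table 5.2.2.2:1*. The reference to the periods is needed because of the follow-up timing in step 3. The rules in Section 5.2.2.1 on test changes and on the term Progressive Disease stay as they are.
2. During source verification, check on a sample of sites that non-serious AEs in the chart were entered in the eCRF. This is a small added task, because Section 8.3.2 does not describe a completeness check.
3. If omissions are found, state in the trial report that the all-grades frequencies by preferred term and the above-5% table are minimum estimates.

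The text change costs a few words in four cells and adds no duty beyond Table 5.2.2.2:1. It does not recover events already left out, which is the reason for the check.
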